### Clinical Assessments

The Structured Clinical Interview for DSM-IV-TR Axis-I Disorders (SCID) and the Schedule for The SCID1 will be administered at baseline to determine study eligibility. The following standard measures will be administered at baseline, both fMRI sessions, and weekly clinic visits:

- The Positive and Negative Affect Schedule is a 20-item questionnaire that measures both positive affect (PA) and negative affect (NA) and is sensitive to subtle changes in affect over time.
- The Hamilton Rating Scale for Depression (HRSD) is a 21-item researcher-rated standardized scale that assesses depressive symptoms and is widely used as a measure of symptom change over time.
- The Inventory of Depression and Anxiety Symptoms (IDAS) is a 64-item self-report questionnaire that comprehensively assesses anxiety and depression symptoms on 10 subscales. The IDAS has excellent psychometric properties and has been validated for assessing reproductive mood disorders.
- The Mood and Anxiety Symptom Questionnaire - Anhedonic Depression Subscale (MASQ-AD) is a 22-item scale that assesses anhedonia (i.e., loss of interest and low positive affect). MASQ-AD scores have been associated with blunted striatal response to reward in previous studies of patients with depression.
- The Greene Climacteric Scale (GCS) is a 21-item scale that is the gold-standard measure of four domains of climacteric symptoms: vasomotor, somatic, anxiety, and depression.
- The Pittsburgh Sleep Quality Index (PSQI) is a 9-item questionnaire that measures the quality and sleep patterns in older adults. \*This measure will only be administered at the two fMRI sessions.

While the SCID and HAM-D are researcher administered, the other measures will be collected through self-report questionnaires using *Qualtrics* or paper and pencil questionnaires.

Despite the use of exclusion criteria designed to reduce risk to participants, depressive symptoms are monitored closely. Any subject who develops severe depressive symptoms (e.g., suicidal ideation) will be discontinued from the study and offered treatment, including inpatient hospitalization.

#### FMRI Tasks

The following task will be included in each of the two fMRI sessions:

The Monetary Incentive Delay (MID) Task engages the reward circuitry during monetary incentive anticipation and outcomes. Each of two MID runs consists of 90 6-second trials during which subjects are presented with one of nine cue shapes, a fixation crosshair (for a variable duration), the target, and performance (win/loss/neutral) feedback. The cue indicates whether it is an incentive (gain, loss) or non-incentive trial. During incentive trials, participants can either gain or lose money by pressing a button during target presentation. Task difficulty is based on participant reaction times. This task elicits reliable frontostriatal dysregulation in people with remitted MDD. Resting state scans will also be conducted at the beginning and end of each session.

The Hariri Emotional Faces Task is an emotional face-matching task that engages neuronal regions implicated in emotional processing, including the amygdala and dorsomedial PFC. This block design paradigm consists of 4 blocks of a perceptual face-processing task interleaved with 5 blocks of a sensorimotor control task. Participants are presented with a target stimulus and asked to select one of 2 images, presented on the low half of the screen, which match the target. Each face-processing block consists of fear and anger sub-blocks. During the sensorimotor control blocks, subjects view a trio of simple geometric shapes. Notably, this task elicited differences in amygdala activation between women with PPD and euthymic postpartum women in a previous study of PPD.

#### Other Tasks

Pizzagalli's Probabilistic Reward Task (PRT) will be conducted outside of the scanner. This task allows us to test the additional hypothesis that perimenopausal depression is characterized by blunted reward learning. During this task, correct identifications of two ambiguous stimuli are differentially rewarded. The task will consist of 300 trials, divided into 3 blocks of 100 trials. Each trial starts with the presentation of a fixation cross for 500 msec followed by a mouthless face. After a delay of 500 msec, either a short mouth (11.5 mm) or a long mouth (13 mm) is presented for 100 msec. Participants will be asked to identify which type of mouth was presented. For each block, the long and short mouths are presented equally often in a pseudorandomized sequence and 40 correct trials are followed by reward feedback immediately after the correct response. An asymmetrical reinforcer ratio will be used in this task, such that for half of the

participants, correct identification of the short mouth will be associated with three times more positive feedback (30 of 40) than correct identification of the long mouth (10 of 40). For the other half of the participants, the contingencies will be reversed.

## 7 Statistical Plan

### 7.1 Sample Size Determination

We approximated power and sample size using a model comparing the two groups on change-scores from baseline to post-treatment. With 20 subjects per group, we have 80% power to detect effect sizes of 0.9, which represents a large effect size. Given our strong preliminary evidence and the experimental nature of the proposed research, we expect to detect statistically significant results. Previous clinical research supports our hypothesized effect size. Studies comparing participants with MDD and controls have yielded effect sizes (Cohen's  $d$ ) ranging from 1.0 to 1.56 in ventral striatum responsivity to reward 51-53. We will enroll an additional 10 participants to account for attrition, increasing the total  $N$  to 50.

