### 7.2 Statistical Methods

This study has one between-subjects factor (group: MDD versus control) crossed with one within-subjects factor (time: baseline versus estradiol treatment) with the outcome (percent signal changed) assessed in response to the MID task in the structurally defined frontostriatal ROIs, including the nucleus accumbens, caudate, thalamus, frontopolar cortex, and dorsolateral prefrontal cortex. Thus, for a task/ROI combination, there is a 2-by-2 repeated measures design. We will analyze this design using an ROI analysis and mixed models with an unstructured covariance structure. To test whether perimenopausal women with MDD show reduced frontostriatal activity (H1) and motivated behavior (H2) in response to reward at baseline, we will examine group differences in BOLD signal and response latency at baseline. To measure the psychological correlates of the frontostriatal response to reward, we will examine change in depressive symptoms between baseline and post-treatment in MDD relative to controls (H3).

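### Section 7.1's 80% power fits one unadjusted change-score test that it does not identify, while 7.2 models at least five unranked regions and 3.2 lists three primary endpoints, with no multiplicity rule

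*Combined protocol and SAP*

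**What the plan says.** - **Power (7.1).** The calculation uses "a model comparing the two groups on change-scores from baseline to post-treatment" and concludes "With 20 subjects per group, we have 80% power to detect effect sizes of 0.9". No alpha, sidedness, endpoint, hypothesis or ROI is given. The support offered is "Studies comparing participants with MDD and controls have yielded effect sizes" (Cohen's d) "ranging from 1.0 to 1.56 in ventral striatum responsivity to reward". The section adds "we expect to detect statistically significant results".
- **Analysis (7.2).** The outcome is percent signal change in frontostriatal ROIs, "including the nucleus accumbens, caudate, thalamus, frontopolar cortex, and dorsolateral prefrontal cortex". The text says that "for a task/ROI combination, there is a 2-by-2 repeated measures design", so each ROI has its own model. None is ranked. For H1 and H2, "we will examine group differences in BOLD signal and response latency at baseline".
- **Endpoints (3.2).** Three primary endpoints are listed without order: frontostriatal reactivity, response latency and depressive symptoms. No ROI and no depression scale is attached to them.
- **Hypotheses (section 2).** H1a names accumbens, caudate and putamen. Putamen is not among the ROIs named in 7.2 or the Study Summary. The five named there are the regions reported from pilot data in item 5 of the Summary of Previous Human Experience.
- **Multiplicity.** No section gives an adjustment, a testing hierarchy, or a statement of which results would count as success.

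**The concern.** A power statement belongs to a specific test. Here the reader cannot tell whether the 80% applies to accumbens, caudate, a frontal region, latency or symptoms. The plan also does not say how many significant ROIs, or which ones, would support Aim 1. As written, one significant ROI out of five or more could be reported as support at a nominal 5% level that does not describe the procedure.

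The effect-size argument has a related gap. The powered test compares change between groups, as in H1b. The cited range compares depressed women with controls, which is the kind of difference H1a concerns.

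At stake is how far the findings can be trusted when they are carried forward. Section 1.1 intends the data to inform a larger placebo-controlled study, and 7.1 expects significance.

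**Working it through.** **1. Reproduce the 80%.** Inputs from 7.1: n = 20 per group and d = 0.9 on change scores. Alpha is not stated, so two-sided 0.05 is assumed.

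- Noncentrality = d × √(n/2) = 0.9 × √10 = 2.846, with 38 degrees of freedom and critical t = 2.024.
- Power = 79.2% by noncentral t, or 81.2% by the normal approximation.
- One-sided 0.05 gives 87.5%, which does not match.
- The effect detectable with exactly 80% power is 0.909 SD of the change score.

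The stated figure therefore fits one unadjusted two-sided 0.05 test.

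**2. False positives across ROIs.** Assume no ROI truly differs and each is tested at 0.05.

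- Independent ROIs, 1 − 0.95^k: five give 1 − 0.95^5 = 22.6%; six (putamen added) give 1 − 0.95^6 = 26.5%.
- Correlated ROIs: simulated two-sample t-tests, 20 per group, equal correlation between ROIs. The documents give no correlations, so these are assumptions.

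| Correlation between ROIs | Five ROIs | Six ROIs |
|---|---|---|
| 0.3 | 21% | 24% |
| 0.5 | 18% | 21% |
| 0.7 | 15% | 17% |
| 0.9 | 10% | 11% |

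These rates are per contrast. Aim 1 has two contrasts: the baseline group difference (H1a) and the difference in change (H1b). Under Holm, the five-ROI rate falls to about 3.5% to 5% for correlations of 0.7 to 0.3.

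**3. If all three primary endpoints are kept.** The first Holm step uses alpha = 0.05/3 = 0.0167, with critical t = 2.505. A two-sample test at d = 0.9 then has these properties:

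- 20 per group: 63.5% power.
- 25 per group (all 50 enrolled complete): 75.6% power.
- 80% power needs 27.3, so 28 per group.

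This is an illustration, not a restated power for the trial. It applies one effect size and one design to hypotheses that differ. H1a has a larger cited d, H2b and H3a are worded as changes within depressed women, and latency carries two hypotheses.

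**4. Does 1.0 to 1.56 support 0.9?** Suppose estradiol reverses a share s of a baseline group difference d₀, net of controls, with equal variances and retest correlation ρ. The standardised difference in change is then s × d₀ / √(2(1 − ρ)). The documents give neither s nor ρ, so the cited range does not determine the change-score effect. The 0.9 is an assumption.

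**The case against.** The strongest reply is that this is a small mechanistic study. Section 1.1 describes it as pilot data for a larger trial, and the objectives include training aims. The ROIs are structurally defined in advance, and section 3.1 puts win against non-win outcomes first and treats anticipation as exploratory. Neighbouring reward regions may be strongly correlated, which lowers the false-positive rate.

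Much of this stands, and it is why the severity is modest. But fixing regions in advance does not rank them, and pilot status does not supply a multiplicity rule for endpoints labelled primary. Even at a correlation of 0.9 the rate is about twice nominal.

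Three further defences also hold in part:

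- **ROI lists.** Both are open-ended, so a reader might infer a contradiction that is not strictly there. What remains is that a hypothesised region is not named for analysis.
- **Difference in change.** A reader might infer that the test of H1b is missing, since 7.2 does not spell it out for BOLD signal or latency. The Study Summary states it, and the group-by-time term of the 7.2 model is that test.
- **Choice of ROI.** Accumbens may look like the obvious primary because it is closest to the cited ventral striatum effect. But that effect is a group difference, and item 4 of the Summary of Previous Human Experience points to dorsolateral and frontopolar cortex for estradiol. The documents do not settle the choice.

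**Conclusion.** The point holds at modest severity. The arithmetic in 7.1 is correct for one test. The defect is that the test is not identified and the analysis around it has no error control. Unadjusted, the chance of at least one false-positive ROI per contrast is about 15% to 21% for five ROIs at assumed correlations of 0.7 to 0.3, about 10% at 0.9, and 23% if independent. The two-sided 0.05 level is inferred from the match in step 1.

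Three stronger conclusions are not supported:

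- **That the trial is underpowered or must enlarge.** Naming one primary test keeps 79% at d = 0.9 with the planned 20 per group. The 64% arises only if three primary tests are kept under Holm and each is a two-sample test at 0.9.
- **That 0.9 is too optimistic.** The cited range does not establish it, but nothing in the documents refutes it.
- **That one favourable region will be picked for the next trial.** The plan does not say so. It only leaves the possibility open.

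**What to change.** 1. **Close the ROI list.** Use the same list in section 2, the Study Summary and 7.2, either adding putamen to the analysis or removing it from H1a.
2. **Name one primary test before analysis,** giving hypothesis, contrast and ROI. State in 7.1 that the 80% refers to it, with two-sided alpha 0.05 and a detectable difference in change of 0.91 SD. If a baseline contrast is chosen, rewrite 7.1 for that contrast. The ROI is the investigators' choice: striatal regions fit the cited group difference for H1a, while the estradiol evidence points to frontal regions.
3. **Place the rest.** Put the other ROIs and endpoints in a Holm-adjusted secondary family, or label them exploratory, and amend 3.2 to match. If all three primaries are kept instead, name the ROI and depression scale, apply Holm across them, and restate power for each test with its own effect size and design. Stated power should then be lowered rather than the sample enlarged.
4. **Restate the support for the effect size.** Say that 1.0 to 1.56 is a group difference relevant to H1a, and that 0.9 on change scores is an assumption.
5. **Minor edits.** Repeat the Study Summary's difference-in-change test for BOLD signal and latency in 7.2. Correct citations 51-53 in 7.1, which lead to papers on hormone therapy and breast cancer.

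Cost: text edits, plus a protocol amendment for the change to 3.2. The other ROIs and endpoints face a stricter threshold or lose confirmatory status.

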### 7.2 Statistical Methods

This study has one between-subjects factor (group: MDD versus control) crossed with one within-subjects factor (time: baseline versus estradiol treatment) with the outcome (percent signal changed) assessed in response to the MID task in the structurally defined frontostriatal ROIs, including the nucleus accumbens, caudate, thalamus, frontopolar cortex, and dorsolateral prefrontal cortex. Thus, for a task/ROI combination, there is a 2-by-2 repeated measures design. We will analyze this design using an ROI analysis and mixed models with an unstructured covariance structure. To test whether perimenopausal women with MDD show reduced frontostriatal activity (H1) and motivated behavior (H2) in response to reward at baseline, we will examine group differences in BOLD signal and response latency at baseline. To measure the psychological correlates of the frontostriatal response to reward, we will examine change in depressive symptoms between baseline and post-treatment in MDD relative to controls (H3).

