**Clinical Assessments**

The Structured Clinical Interview for DSM-IV-TR Axis-I Disorders (SCID) and the Schedule for The SCID1 will be administered at baseline to determine study eligibility. The following standard measures will be administered at baseline, both fMRI sessions, and weekly clinic visits:

- The Positive and Negative Affect Schedule is a 20-item questionnaire that measures both positive affect (PA) and negative affect (NA) and is sensitive to subtle changes in affect over time.
- The Hamilton Rating Scale for Depression (HRSD) is a 21-item researcher-rated standardized scale that assesses depressive symptoms and is widely used as a measure of symptom change over time.
- The Inventory of Depression and Anxiety Symptoms (IDAS) is a 64-item self-report questionnaire that comprehensively assesses anxiety and depression symptoms on 10 subscales. The IDAS has excellent psychometric properties and has been validated for assessing reproductive mood disorders.
- The Mood and Anxiety Symptom Questionnaire - Anhedonic Depression Subscale (MASQ-AD) is a 22-item scale that assesses anhedonia (i.e., loss of interest and low positive affect). MASQ-AD scores have been associated with blunted striatal response to reward in previous studies of patients with depression.
- The Greene Climacteric Scale (GCS) is a 21-item scale that is the gold-standard measure of four domains of climacteric symptoms: vasomotor, somatic, anxiety, and depression.
- The Pittsburgh Sleep Quality Index (PSQI) is a 9-item questionnaire that measures the quality and sleep patterns in older adults. \*This measure will only be administered at the two fMRI sessions.

While the SCID and HAM-D are researcher administered, the other measures will be collected through self-report questionnaires using *Qualtrics* or paper and pencil questionnaires.

Despite the use of exclusion criteria designed to reduce risk to participants, depressive symptoms are monitored closely. Any subject who develops severe depressive symptoms (e.g., suicidal ideation) will be discontinued from the study and offered treatment paid for by the study. If inpatient hospitalization becomes

necessary as a result of the study, UNC Health Care will cover the cost. The following language has been added to the study consent form to reflect this policy:

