## **4 Subject Selection and Withdrawal**

### **4.1 Inclusion Criteria**

Participants will include healthy, unmedicated perimenopausal women ages 44-55 either with ( $n=20$ ) or without ( $n=20$ ) current major depression. Thus, only participants capable of giving informed consent will be enrolled. Participants will be compensated upon completion of the study.

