### 5.3 Method for Assigning Subjects to Treatment Groups

This is a case-control study design, and all subjects will receive the same drug protocol.

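### H1a and H2a compare unmatched, non-randomised groups at baseline with no covariate; adding age, and one vasomotor sensitivity analysis, is a cheap improvement

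*Combined protocol and SAP*

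**What the plan says.** Section 5.3 states "This is a case-control study design, and all subjects will receive the same drug protocol". Group is thus a diagnosis and not an allocation. Sections 4.1 to 4.3 recruit "healthy, unmedicated perimenopausal women ages 44-55" and describe no individual or frequency matching. According to the Study Summary, controls meet the case criteria except for psychiatric history.

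Section 7.2 and the Study Summary give the model: "This study has one between-subjects factor (group: MDD versus control) crossed with one within-subjects factor (time: baseline versus estradiol treatment". H1a (reward-related BOLD) and H2a (response latency) are tested as group differences at baseline. Time does not enter that contrast, so group is its only explanatory variable. Neither section names a covariate, stratification factor or sensitivity analysis.

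The data for an adjustment are already collected. Age is an eligibility variable. Table 1 schedules the Greene Climacteric Scale (GCS) at visits 1 and 3 to 6, and visit 3 is the baseline scan. The protocol calls the scale the "gold-standard measure of four domains of climacteric symptoms: vasomotor, somatic, anxiety, and depression". The PSQI is taken at both scans. None of these enters any stated analysis.

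Sections 1.1 and 3.1 use the baseline difference to examine the role of frontostriatal hypoactivity in the pathophysiology of perimenopausal depression.

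**The concern.** In a non-randomised comparison, any variable that differs between the groups and is related to the outcome is carried into the group effect. Two candidates stand out. Age may vary over 11 years (44 to 55) in each group. Vasomotor burden has no eligibility limit.

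H1a and H2a are more exposed than H1b. H1b compares changes, so each woman is her own control and a stable additive effect of age drops out. The baseline contrasts have no such protection, and H1a carries the first half of the central hypothesis in Section 2, that the reward system is hypoactive in perimenopausal MDD. If the groups differed systematically in age or hot flushes, the plan has no step that would show it or allow for it.

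**Working it through.** **1. The plan's own figure.** Section 7.1 says "With 20 subjects per group, we have 80% power to detect effect sizes of 0.9", based on this approach: "We approximated power and sample size using a model comparing the two groups on change-scores from baseline to post-treatment". No alpha is stated; I assume 0.05 two-sided. With n = 20 per group the standard error of a standardised difference is √(2/20) = 0.316, so the noncentrality at d = 0.9 is 0.9/0.316 = 2.85. On 38 df this gives 79.2% power (81.2% by the normal approximation). One-sided 0.05 gives 87.5% and does not fit. The 80% reproduces as an unadjusted two-sided comparison. Section 7.1 applies it to change scores; I use the same formula below for the baseline contrasts.

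**2. Systematic imbalance.** Let D be the true group difference in a covariate, in SD units, and r its within-group correlation with the outcome. The documents give neither, so both are assumed. With no true MDD effect, the expected standardised group difference is r × D, and the two-sided rejection rate comes from the noncentral t with noncentrality r × D × √10:

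| D | r | Spurious d | Noncentrality | Rejection rate |
|---|---|---|---|---|
| 0.3 | 0.2 to 0.5 | 0.06 to 0.15 | 0.19 to 0.47 | 5.4% to 7.5% |
| 0.5 | 0.3 | 0.15 | 0.47 | 7.5% |
| 0.8 | 0.4 | 0.32 | 1.01 | 16.7% |
| 1.0 | 0.5 | 0.50 | 1.58 | 33.8% |

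Simulation of the last three rows gave 7.7%, 17.1% and 33.4%. With the covariate in the model the rates were 5.1%, 5.1% and 4.9%.

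The bias can also hide an effect. A true d of 0.9 offset by 0.15 is seen as 0.75; the noncentrality is 0.75 × √10 = 2.37 and power falls from 79.2% to 63.7%.

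**3. Chance imbalance.** If the source populations are alike, the probability of an imbalance of at least 0.5 SD at 20 versus 20 is 2 × [1 − Φ(0.5/0.316)] = 11.4%. For 0.8 SD it is about 1.1%. This variation is already part of the outcome variance, so the crude test keeps its 5% error rate on average.

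**4. Scale for age.** If age were uniform over 44 to 55 (an assumption), its SD would be 11/√12 = 3.2 years, and 0.5 SD would be about 1.6 years.

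**5. Cost of adjusting.** The variance of the adjusted group effect is (1 − R²) × (2/n + D²/(2n − 2)). With R² = 0 and D = 0.5 this is 0.1 + 0.25/38 = 0.1066, so the standard error is 0.326 and the noncentrality at d = 0.9 is 2.76. On 36 df (two covariates) power is 76.5%; on 37 df (one covariate) it is 76.6%. Two-covariate power in other cases:
- no imbalance, R² = 0: 79.1%
- D = 0.5, R² = 0.10: 80.7%
- D = 1.0, R² = 0: 69.3%

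**The case against.** **Restriction already does much of the work.** Both groups must be in the late transition, with raised FSH, BMI within limits, a final menstrual period no more than 12 months earlier, no smoking and no excluded medication, and they come through the same recruitment channels. This stands for age and reproductive stage, and the documents give no reason to expect the groups to differ in age. It does not cover vasomotor symptoms.

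**The outcomes are within-person contrasts.** BOLD is win versus non-win and latency is reward versus non-reward, so general slowing or a global signal change would largely cancel. This stands in part. A covariate related to the reward response itself does not cancel. For latency, H2a predicts slowing on reward trials only, but Section 7.2 states no group-by-trial-type test, so removal of general slowing is not assured.

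**Vasomotor symptoms may share a cause with the depression.** The protocol presumes that ovarian hormone withdrawal is the cause of perimenopausal MDD, and adjusting for another of its consequences could distort the group effect. This stands, and it rules the vasomotor score out of the primary model.

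**A reader might infer more from the 11% chance-imbalance figure**, namely that the crude test has an inflated error rate. It does not. Chance imbalance widens the spread of estimates and leaves the average error rate at 5%. Only systematic imbalance biases H1a and H2a.

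**The study is described in Section 1.1 as providing pilot data** for a larger randomised, placebo-controlled study. That lowers the stakes, but the same section reads the baseline difference as pathophysiology.

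**Conclusion.** The baseline contrasts for H1a and H2a are unmatched and unadjusted while being given a pathophysiological reading. Confounding by age is narrowed by design but not excluded, and confounding by vasomotor burden is not addressed. The possible bias runs in either direction. Its size rests wholly on assumed r and D: slight at 0.3 SD, a 7.5% false-positive rate at r = 0.3 and 0.5 SD, and 16.7% at r = 0.4 and 0.8 SD.

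A reader might infer that age or hot-flush differences will in fact be reported as reward hypoactivity or slowing due to MDD. The documents do not support that: they show no such imbalance and give no correlation with the outcomes. What they support is that the plan would neither reveal nor allow for such a difference if it were present. This is a cheap improvement and not a flaw that invalidates the design.

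**What to change.** - In Section 7.2 and the Study Summary, add age as a fixed covariate in the models for BOLD and for response latency.
- Pre-specify one sensitivity analysis of H1a and H2a that also includes the visit 3 GCS vasomotor subscale. Use the subscale and not the total score, which contains anxiety and depression domains. Keep the vasomotor score, the GCS mood subscales and sleep out of the primary model, because they may share a cause with MDD or be part of it.
- Tabulate age, vasomotor score and PSQI by group.

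Naming the covariates in advance also prevents a later choice among adjustments. The cost is SAP wording, one table and one degree of freedom in the primary model (two in the sensitivity analysis). There is also some loss of power if the covariates are imbalanced but unrelated to the outcome: at d = 0.9, 76.5% with two covariates and 0.5 SD imbalance, against 79.2% unadjusted. Covariates that explain 10% of the variance would recover this (80.7%). No new data are needed.
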